8.5 STUDY PROCEDURES AND ASSESSMENTS

8.5.1 Study Procedures

Approximately 40 study visits are scheduled for screening, treatment and for assessment of safety, efficacy and pharmacokinetics as depicted in the study flow chart (see §2.2) and summarised below. The End of Study Visit is scheduled 180 days after Visit 1/Day 1.

Written Informed Consent has to be obtained PRIOR to performing any study assessment, as described below:

Screening Period (Day -7 to 0)

- Check of Inclusion/Exclusion Criteria
- Demographic data collection
- Medical and medication general history
- AML history, i.e. date of onset of AML, relapsed or refractory status following the last AML treatment, de novo or secondary AML status, number and category of previous AML treatments (including autologous and allogeneic HSCT), and duration of last CR (for relapsed patients), and disease features when available (i.e. AML karyotype, NPM1 and/or FLT3-ITD mutational status, FAB subtype)
- Physical examination, including vital signs (i.e. blood pressure [BP], heart rate [HR], breathing rate [BR], body temperature [T])
- Weight measurement
- Performance Status (PS) evaluation
- 12-lead ECG
- Blood sampling and urine collection for safety lab tests, including pregnancy test (if applicable)
- Blood sampling for anti-HIV antibodies, anti-HBcAg antibodies, HBV-DNA, HCV-RNA
- •

- Blood sampling for immunogenicity assessment
- -
- Bone marrow aspirate for morphologic assessment,
- Recording of AEs and change in concomitant medication

NOTE: Results of laboratory tests for anti-HIV antibodies, anti-HBcAg antibodies, HBV-DNA, HCV-RNA which have been performed within 3 months prior to Screening Period in the context of the standard patient's management (either in the local lab or in a different lab, provided that they comply with local standard procedures) can be reported in the e-CRF under Screening Period procedures and added in the patient file as source documents. In such case, there is no need to repeat the above mentioned tests.

TREATMENT PHASE

CYCLE 1

Visit 1/Day 1, first 3-day "ramp-up" dose

Prior to study drug administration

- Re-check inclusion/exclusion criteria and confirmation of patient's eligibility prior to start treatment
- Physical examination, including vital signs
- Weight measurement
- PS evaluation
- 12-lead ECG
- Blood sampling and urine collection for safety lab test NOTE: Check that WBC count is ≤ 10 x 10⁹/L; hydroxyurea is allowed to lower WBC count.
- Blood sampling for PK (pre-infusion)
- Recording of AEs and change in concomitant medications
- TLS risk assessment (see Appendix I: TLS Manual for Investigator)
- TLS prophylaxis (see Appendix I: TLS Manual for Investigator)
- Premedication (see §8.4.2)

Study drug administration

- Study drug administration, given as a 6 h infusion with constant infusion rate
- Blood sampling for safety lab test at following time points after start of infusion: 2h, 4h, 8h, 12h.
- Vital signs every 15 minutes during the first hour of study drug administration and then at the same time points of blood sampling for safety lab test

- 12-lead ECG at the end of infusion
- Blood sampling for PK (at the end of infusion, and 6h after the end of infusion)
- Recording of AEs and change in concomitant medications

Visit 2/Day 2(one day after the completion of Visit 1) and Visit 3/Day 3 (one day after the completion of Visit 2)

Prior to study drug administration

- Physical examination, including vital signs
- PS evaluation
- 12-lead ECG
- Blood samplingfor safety lab test
- Blood sampling for PK (pre-infusion)
- Recording of AEs and change in concomitant medications
- TLS prophylaxis (see *Appendix I: TLS Manual for Investigator*)
- Premedication (see §8.4.2)

Study drug administration

- Study drug administration, given as 6h infusion with constant infusion rate
- Blood sampling for safety lab test at the following time points after start of infusion: 2h, 4h, 8h, 12h
- Vital signs every 15 minutes during the first hour of study drug administration and then at the same time points of
 - blood sampling for safety lab test
- 12-lead ECG at the end of infusion
- Urine collection at the end of infusion (ONLY at Visit 3)
- Blood sampling for PK
 at the end of infusion, 6h after the end of infusion (ONLY at Visit 2), 14h after the end of infusion (ONLY at Visit 3)
- Recording of AEs and change in concomitant medications

Visit 4/Day 4, one day after the completion of the entire first *"ramp-up"*

- Physical examination, including vital signs
- PS evaluation
- Blood sampling for safety lab test
- •
- Blood sampling for PK infusion

24h after the end of last "ramp-up" dosing

Bone marrow aspirate for morphologic assessment,

Recording of AEs and change in concomitant medications

Visit 5-6/Day 5-6, one and two days after Visit 4, respectively

- Blood sampling for PK
 (44h and 68h after the end of last "*ramp-up*" dosing infusion)
- Recording of AEs and change in concomitant medications

Visit 8/Day 8 (five days after the completion of Visit 3), Visit 9/Day 9 (one day after the completion of Visit 8) and Visit 10/Day 10 (one day after the completion of Visit 9), second 3-day "*ramp-up*" administration

Prior to study drug administration

- Physical examination, including vital signs
- Weight measurement (ONLY at Visit 8/Day 8)
- PS evaluation
- Blood sampling for safety lab test NOTE: Check that WBC count is ≤ 10 x 10⁹/L (ONLY at Visit 8/Day 8); hydroxyurea is allowed to lower WBC count.
- Blood sampling for PK (pre-infusion)
- Recording of AEs and change in concomitant medication
- TLS prophylaxis (see Appendix I: TLS Manual for Investigator)
- Premedication (see §8.4.2)

Study drug administration

- Study drug administration, given as a 6h infusion with constant infusion rate
- Blood sampling for safety lab test at the following time points after start of infusion: 2h, 4h, 8h, 12h
- Vital signs every 15 minutes during the first hour of study drug administration, after then at the same time points of blood sampling for safety lab test
- Blood sampling for PK
 at the end of infusion)
- Recording of AEs and change in concomitant medications

Visit 11/Day 11, one day after the completion of the entire second "ramp-up"

- Physical examination, including vital signs
- PS evaluation
- Blood sampling for safety lab test including pregnancy test, if applicable
- Recording of AEs and change in concomitant medications

Visit 12/Day 15, five days after Visit 10, first "one-shot" infusion

Prior to study drug administration

- Physical examination, including vital signs
- Weight measurement
- PS evaluation
- Blood sampling for safety lab test

NOTE: Check that WBC count is $\leq 10 \ge 10^{9}$ /L; hydroysurea is allowed to lower WBC count.

- Blood sampling for PK (pre-infusion)
- Recording of AEs and change in concomitant medications
- TLS prophylaxis (see Appendix I: TLS Manual for Investigator)
- Premedication (see §8.4.2)

Study drug administration

- Study drug administration, given as a 6h infusion with constant infusion rate
- Blood sampling for safety lab test at the following time points after start of infusion: 2h, 4h, 8h, 12h
- Vital signs every 15 minutes during the first hour of study drug administration, after then at the same time points of blood sampling for safety lab test
- Blood sampling for PK (at the end of infusion)
- Recording of AEs and change in concomitant medications

Visit 13-15/Day 16-18, one, two and three days after Visit 12

- Physical examination including vital signs
- PS evaluation
- Blood sampling for safety lab test (at 24h, 48h and 72 h after start of infusion)
- Recording of AEs and change in concomitant medications

CYCLE 2

Visit 16/Day 22, seven days after Visit 12

Prior to study drug administration

- Physical examination including vital signs
- Weight measurement
- PS evaluation
- Blood sampling for safety lab test
- •
- Blood sampling for PK

(pre-infusion)

- Bone marrow aspirate for morphologic assessment,
- Recording of AEs and change in concomitant medications
- Premedication (see §8.4.2)

Study drug administration

- Study drug administration, given as a 6h infusion with constant infusion rate
- Vital signs every 15 minutes during the first hour of study drug administration and at 15 minutes after end of infusion
- Blood sampling for PK (at the end of infusion)
- Recording of AEs and change in concomitant medications

Visit 17-19/ Day 23-25, one, two and three days after the completion of Visit 16, respectively

- Physical examination including vital signs
- PS evaluation
- Blood sampling for safety lab test
- Recording of AEs and change in concomitant medications

Visit 20/Day 29, seven days after the completion of Visit 16

Prior to study drug administration

- Physical examination including vital signs
- Weight measurement
- PS evaluation
- Blood sampling for safety lab test
- Blood sampling for PK (pre-infusion)
- Recording of AEs and change in concomitant medication
- Premedication (see §8.4.2)

Study drug administration

- Study drug administration, given as a 6h infusion with constant infusion rate
- Vital signs every 15 minutes during the first hour of study drug administration and at 15 minutes after end of infusion
- Blood sampling for PK
 at the end of infusion
- Recording of AEs and change in concomitant medications

Visit 21-23/Day 30-32, one, two and three days after the completion of Visit 20, respectively

- Physical examination including vital signs
- PS evaluation
- Blood sampling for safety lab test
- Recording of AEs and change in concomitant medications

Visit 24/Day 36, seven days after the completion of Visit 20

Prior to study drug administration

Physical examination including vital signs

- Weight measurement
- PS evaluation
- Blood sampling for safety lab test
- Blood sampling for PK (pre-infusion)
- Recording of AEs and change in concomitant medications
- Premedication (see §8.4.2)

Study drug administration

- Study drug administration, given as a 6h infusion with constant infusion rate
- Vital signs every 15 minutes during the first hour of study drug administration and at 15 minutes after end of infusion
- Blood sampling for PK (at the end of infusion and at 1h and 6h after the end of infusion)
- Recording of AEs and change in concomitant medications

Visit 25-27/Day 37-39, one, two and three days after the completion of Visit 24, respectively

- Physical examination including vital signs
- PS evaluation
- Blood sampling for safety lab test including pregnancy test (only at Visit 27, if applicable)
- Blood sampling for PK (24h, 48h and 72h after the end of infusion)
- Recording of AEs and change in concomitant medications

Visit 28-29/Day 40-41, one and two days after Visit 27, respectively

- Blood sampling for PK (96h and 120h after the end of infusion)
- Recording of AEs and change in concomitant medications

Visit 30/Day 42, the day after Visit 29

- Physical examination including vital signs
- PS evaluation
- Blood sampling for safety lab test
- . .
- Blood sampling for PK

(144h after the end of infusion)

- Bone marrow aspirate for morphologic assessment,
- Recording of AEs and change in concomitant medications

NOTES:

- During Cycle 1, under the *"ramp-up"* dosing scheme, an administration visit will encompass the three *"ramp-up"* infusions (to be split in up to four days, in case of specific infusion-related toxicities, see §8.4.7) to complete the administration of MEN11112.
- Prior to start MEN1112 infusion, results of the safety lab tests (including hepatic function tests) should be duly checked by the Investigator to confirm that eligibility criteria are met (Visit 1/Day 1, prior of infusion) or no treatment withdrawal/dose interruption criteria are met (any subsequent infusion).
- One of the following adjustments is allowed:
 - +1 day for any "*ramp-up*" administration visit in case of WBC count $>10 \times 10^{9}$ /L on the first day of such visit, in order to lower the WBC count using hydroxyurea. This is applicable also to the "*one-shot*" infusion visit of Cycle 1 (Visit 12/Day 15).
 - + 1 day for each study drug administration visit (i.e. first *"ramp-up"* and *"one-shot"* administration visit).
- In case of study visit re-schedule due to infusion related toxicities (see §8.4.7), WBC count recovery, or any other reasons, the interval of 5 days (Cycle 1) or 7 days (Cycle 2) between the end of any study drug administration visit and the start of the following one should be guaranteed.
- Moreover, at each infusion during the study conduct, in case of interruption due to drugrelated toxicities:
 - The infusion duration will be prolonged **constant infusion rate**; this infusion duration will then be applied to every subsequent infusions.
 - In case the interruption lasts >24 hours, the safety assessments will be repeated when the infusion is resumed according to the time-points scheduled for the original visit.
 - If any interruption occurs during Cycle 1 and the 3rd infusion of Cycle 2, blood sampling for PK & exploratory tests will also be taken at the time of each infusion interruption and just before each infusion resumption.
- During Cycle 1, under the "ramp-up" dosing scheme, prior to start each administration visit WBC count should be ≤ 10 x 10⁹/L. In case the "ramp-up" administration visit is split due to infusion-related toxicities, WBC count should be ≤ 10 x 10⁹/L also prior to start the second part of the "ramp-up" administration visit.
- During Cycle 1, patients must be treated and monitored as in-patients up to at least 24 hours after each study drug administration visit.
- As the consumption of fibrinogen is a marker of disseminated intravascular coagulation, the Investigator shall carefully monitor the fibrinogen decrease rate and consider prompt

treatment with fresh frozen plasma even in the presence of fibrinogen values within normal range.

END of TREATMENT

Visit 31-34/Day 43/50/57/64, one week, two weeks, three weeks and four weeks after Visit 24, respectively)

- Blood sampling for PK
- Blood sampling for immunogenicity assessment (ONLY at Visit 34)
- Recording of AEs and change in concomitant medications

NOTE: During the End of Treatment, a time-frame of + 1 day is allowed at any visit, however the scheduled time of the following visits should be maintained.

FOLLOW-UP PERIOD

Visit 35-38/Day 65/85/121/149, one, twenty-nine, fifty-seven and eighty-five days after Visit 34, respectively

- Physical examination, including vital signs
- PS evaluation
- Blood sampling for safety lab test including pregnancy test (if applicable)
- Bone marrow aspirate for morphologic assessment on Visit 35 and Visit 37 only in patients showing peripheral blood labs consistent with CR/CRi/PR
- Recording of AEs and change in concomitant medications.

NOTES:

- To serve the best interest of the patients, for those achieving at least a partial remission, the Sponsor commits to consider providing MEN1112 to allow the prosecution of the infusions at the frequency recommended by the iDSMB on an individual basis and after discussion with the treating Investigator and the Medical Monitor. In this case, premedication and safety assessments will resemble those already described for study drug administration visits, unless differently advised by the iDSMB.
- During Follow-up Period, a time-frame of + 2 days each is allowed at any visit, however the scheduled time of the following visits should be maintained.

END OF STUDY

End of Study Visit (180 days after Visit 1/Day 1)

- Physical examination and vital signs
- PS evaluation
- Blood sampling for safety lab test including pregnancy test (if applicable)
- .

- Bone marrow aspirate for morphologic assessment,
- Recording of AEs and change in concomitant medications

NOTES:

- At the End of Study Visit, a time-frame of + 5 days is allowed.
- All patients shall undergo the End of Study Visit at the scheduled date or at the time of study withdrawal. Unscheduled assessments showing disease progression and leading to patient's withdrawal can replace the End of Study Visit provided that all assessment/procedures scheduled for this visit are completed.
- In case the patient is discontinued from the study within the treatment period, the End of Study Visit bone marrow aspirate is highly recommended to be performed.

GENERAL NOTES:

- For each safety lab test, blood sampling for PK (except for those to be collected at the end of infusion) and for vital signs, a window of +/- 5% of the required time interval is allowed.
- The total dose calculated for the first study drug administration can be applied also for the following ones providing that actual patient's weight is within ±10% of the weight measured prior to the first study drug administration; otherwise, the total dose to be given shall be calculated based on the weight measured at the corresponding visit.
- Any effort aimed at preserving patient's safety and/or further clarifying an adverse event is recommended, including unscheduled assessments (e.g. additional safety lab sampling, additional safety lab parameters). The anonymized documentation of the above unscheduled assessment shall be then provided to the Sponsor.
- It is strongly recommended not to start the treatment on the day prior to -or onweekends/holidays, unless the treatment is deemed not deferrable by the Investigator in view of the specific patient's clinical situation. In such case, the site shall anyway guarantee the actual availability of site personnel as well as the actual feasibility of ALL study procedures as required by the protocol.

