to infusion-related toxicities. WBC count should be $\leq 10 \text{ x}$
$10^9/\text{L}$ also prior to start the second part of the "ramp-up"
administration visit
 During Cycle 1 patients must be treated and monitored as in
• During Cycle 1, patients must be treated and monitored as in-
patients up to at least 24 hours after each study drug
administration visit.
• As the consumption of fibrinogen is a marker of disseminated
intravascular coagulation, the investigator shall carefully
monitor the fibrinogen decrease rate and consider prompt
treatment with fresh frozen plasma even in the presence of
fibrinogen values within normal range.
END of TREATMENT
Visit 31-34/Day 43/50/57/64, one week, two weeks, three weeks
and four weeks after Visit 24, respectively
 Blood sampling for PK
 Blood sampling for immunogenicity assessment (ONLY
at Visit 34)
 Recording of AEs and change in concomitant medications
NOTE : During the End of Treatment, a time-frame of + 1 day is
allowed at any visit, however the scheduled time of the following

visits should be maintained.
FOLLOW-UP PERIOD
Visit 35-38/Day 65/85/121/149, one, twenty-nine, fifty-seven and
eighty-five days after Visit 34, respectively
 Physical examination, including vital signs
 PS evaluation
 Blood sampling for safety lab test including pregnancy
test (if applicable)
 Bone marrow aspirate for morphologic assessment on
Visit 35 and Visit 37 only in patients showing peripheral
blood labs consistent with CR/CRi/ Partial Remission
(PR)
 Recording of AEs and change in concomitant medications
NOTES:
- To serve the best interest of the patients, for those
achieving at least a partial remission, the Sponsor
commits to consider providing MEN1112 to allow the
prosecution of the infusions at the frequency
recommended by the iDSMB on an individual basis
and after discussion with the treating Investigator and
the Medical Monitor. In this case, premedication and
safety assessments will resemble those already
described for study drug administration visits, unless
differently advised by the iDSMB.
- During Follow-up Period, a time-frame of + 2 days
each is allowed at any visit, however the scheduled
time of the following visits should be maintained.
END OF STUDY
End of Study Visit (180 days after Visit 1/Day 1)
 Physical examination and vital signs
 PS evaluation
 Blood sampling for safety lab test including pregnancy

test (if applicable)
Bone marrow aspirate for morphologic assessment

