a = Inclusion criteria will be evaluated during the Screening Period, with the exception of inclusion criteria 3 and 4, which will be evaluated at Visit 1/Day1; inclusion criteria 5 and 6 will be re-evaluated prior to the first study drug administration (Visit 1/Day1).

Exclusion criteria will be evaluated during the Screening Period, with the exception of exclusion criteria 6, 7, 8 and 9, which will be evaluated at Visit 1/Day 1; exclusion criteria 4 and 5 will be re-evaluated prior to the first study drug administration (Visit 1/Day 1).

b = Performance status evaluation according to ECOG scale.

c = Vital signs to be collected prior to study drug administration and every 15 minutes during the first hour of study drug administration and then at the same time points of blood sampling for safety lab tests.

d = Vital signs to be collected prior to study drug administration and every 15 minutes during the first hour of study drug administration and 15 minutes after the end of infusion.

e = Weight measurement ONLY prior to the first "ramp-up" dose.

f = 12-Lead-ECG should be performed prior to study drug administration and at the end of infusion.

g = Safety lab tests will be performed locally, to guarantee the management of the patient (the specific time points are listed in *Appendix III: Timings of safety blood sampling*).

- h = Check of WBC count $\leq 10 \times 10^9$ L prior to the first "*ramp-up*" study drug administration (Visit 1/Day 1, Visit 8/Day 8) and at Visit 12/Day 15; hydroxyurea is allowed to lower WBC count.
- i = In case the "*ramp-up*" administration visit is split due to infusion-related toxicities, WBC count should be $\leq 10 \times 10^9$ /L also prior to start the second part of the "*ramp-up*" administration visit.

k = Blood sampling for immunogenicity assessment to be collected during the Screening Period (Day -7 to Day 0) and at Visit 34.

- 1 =
- m = Blood sampling for anti-HIV antibodies, anti-HBcAg antibodies, HBV-DNA, HCV-RNA to be tested according to local standard procedures ONLY in case results of laboratory tests for have not been performed within 3 months prior to Screening Period.
- n = Blood sampling for CD157 receptor occupancy assessment.
- o = Bone marrow aspirate for morphologic assessment, discontinued from the study within the treatment period, the End of Study Visit bone marrow aspirate is highly recommended to be performed.

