6.2.4.3 Overview of clinical pharmacokinetics

MEN1112 serum concentrations from Cohort 0.1 mg/kg to Cohort 1.7 mg/kg of ARMY-1 study were measured and an interim PK analysis was performed for 38 subjects after a single IV infusion and for 8 subjects after six consecutive IV infusions. The pharmacokinetics of MEN1112 in human were characterised by a dose-dependent behaviour after both single and repeat dose administration, as shown by a more than proportional increase in AUC_{0-inf} in the dose-range 0.1-2.5 mg/kg. MEN1112 was slowly cleared from the body, with a mean half-life ranging from 10.8 to 41.8 hr and from 12.8 to 146.4 hr after single and repeat dose, respectively. The values obtained for volume of distribution at steady state were similar to total blood volume (i.e. 5 L). Estimates of clearance were also low (0.02 - 0.9 L/hr) and in the range of those reported for other monoclonal antibodies. The magnitude of inter-individual variability in MEN1112 disposition is large in the explored dose-range of 0.1-2.5 mg/kg.

6.3 **RISK BENEFIT ASSESSMENT**

The medical need for AML and MDS is yet highly unmet and new treatments are urgently needed for either disease.

MEN1112 is a defucosylated Monoclonal Antibody with high affinity binding to Bst1/CD157 antigen, which is expressed at high prevalence on both AML and MDS cells.

Due to its ability to deplete AML and MDS blasts, even in the presence of low NK cells percentage, MEN1112 is considered to have the potential to represent a new targeted therapeutic opportunity in both AML and MDS patients. the single agent activity of MEN1112 is under clinical investigation in patients with relapsed or refractory AML in the ARMY-1 trial. In this trial, the MTD of the "*one-shot*" administration schedule has been identified at 1.7 mg/kg following the occurrence of two DLT events in two patients treated at 2.5 mg/kg dose level

. The Sponsor therefore performed an in-depth review of the safety

profile of MEN1112, with a particular focus on the four patients

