8.2.3 Withdrawal of patients from therapy or assessment

Participation in the study is strictly voluntary and patients have the right to withdraw from the study at any time without explanation. This will not affect his/her rights for future medical care. Treatment should be discontinued also if this is in the best interest of the patient upon Investigator judgement and/or in case of any of the following:

- Non-compliance of the patient or investigator with the protocol
- Disease progression
- DLTs
- Infusion toxicities requiring permanent treatment discontinuation (see §8.4.7)
- Treatment-related grade 3 not haematological toxicity lasting more than 7 days occurring after the first cycle, excluding common complications of AML (in particular infections, bleedings, fatigue)
- Treatment-related grade \geq 4 not haematological toxicity occurring after the first cycle, excluding common complications of AML (in particular infections, bleedings, fatigue)
- Life threatening related Serious Adverse Event (SAE)
- Patient receives other treatment for AML (including HSCT)
- Occurrence of pregnancy

The Investigator is ultimately responsible for the safety and well-being of the patients and, if at any time during the study it is believed that the constraints of this protocol are detrimental to the patient's health, the patient may be withdrawn from the study.

Withdrawal of a patient must be notified to the study monitor, the reason(s) of withdrawal should be documented in the e-CRF and follow-up should be reported. For patients who withdraw from study, End of Study Visit has to be performed at the time of withdrawal.

If a patient prematurely terminates the study, data already collected will be used and analysed for the purpose of the study. In regard to biological samples already collected, in case of Informed Consent withdrawal, the patient may choose if samples not yet analysed, shall be analysed or destroyed.

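### The only post-baseline anti-MEN1112 antibody sample is at Visit 34 (Day 64), with none at the withdrawal visit, so patients who withdraw earlier drop out of the immunogenicity endpoint

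*Combined protocol and SAP*

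**What the plan says.** Immunogenicity is a secondary objective (7.2), and the incidence of anti-MEN1112 antibodies is a secondary endpoint (8.5.4.2). Three places give the sampling times, and they agree.

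- Flow-chart note k (2.2): "Blood sampling for immunogenicity assessment to be collected during the Screening Period (Day -7 to Day 0) and at Visit 34".
- Procedures (8.5.1, End of Treatment): "Blood sampling for immunogenicity assessment (ONLY at Visit 34".
- The synopsis carries the same restriction: "Blood sampling for immunogenicity assessment (ONLY", again followed by Visit 34.

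Visit 34 is anchored to the last planned administration: "Visit 31-34/Day 43/50/57/64, one week, two weeks, three weeks and four weeks after Visit 24, respectively".

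On withdrawal, 8.2.3 states: "For patients who withdraw from study, End of Study Visit has to be performed at the time of withdrawal". Blood is drawn at that visit: "Blood sampling for safety lab test including pregnancy test (if applicable" is on its list in 8.5.1. Its blood-sampling cell in the flow chart carries only code n, which is "Blood sampling for CD157 receptor occupancy assessment". No immunogenicity sample is listed.

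Section 8.6.6 requires at least ten weeks of follow-up after the last dose for patients who stop treatment, but attaches no antibody sample. The general notes in 8.5.1 recommend unscheduled assessments to clarify an adverse event, without naming antibodies. Section 9.3.5 rules out imputation and applies observed cases to all analyses. Section 9.2 defines no immunogenicity population.

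**The concern.** With a single post-dose time point four weeks after the final planned infusion, the endpoint can be measured only in patients still on study at Day 64. A patient who withdraws earlier has a Screening sample and nothing to compare it with. A patient who stops treatment before Visit 24 but stays in follow-up is also badly served, because the visit from which Visit 34 is counted never takes place.

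Two things are at stake. The first is precision: the number of results may be well below the number treated. The second is selection: the incidence would describe those who stayed on study to Day 64 and be silent on those who left. An observed-cases summary does nothing about the second problem, and the missing samples cannot be recovered after the trial.

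**Working it through.** **1. Is the gap real, or an effect of redaction?** Some flow-chart notes are blacked out, but note k is legible and lists both time points. Code k appears in the blood-sampling row only at Screening and in the Visit 31-34 column. The End of Study cell has code n alone. The gap is in the plan.

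**2. Timing.** Visit 34 is Day 64 and Visit 24 is Day 36. 64 − 36 = 28 days, matching the stated four weeks. Visit 24 is the sixth planned administration, counting each three-day ramp-up as one (three in Cycle 1, three in Cycle 2).

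**3. The plan's own figures, reproduced.** From Table 1 in 6.2.4.1:

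- Early withdrawal: 4 + 7 + 6 + 8 + 10 + 5 = 40 of 4 + 7 + 6 + 8 + 17 + 5 = 47, or 85.1%, as stated.
- Efficacy population: 2 + 4 + 5 + 4 + 5 + 2 = 22 of 47, or 46.8%, as stated.

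Section 6.2.4.3 reports an interim PK analysis in 38 subjects after one infusion and "for 8 subjects after six consecutive IV infusions": 8/38 = 21.1%. Section 9.1 assumes 30% drop-out and about 60 treated patients.

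**4. Share reaching Visit 34.** No document states it, so three scenarios are set out, each an assumption:

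- 70%, from the 30% drop-out in 9.1. That section does not tie the figure to Day 64.
- 46.8%, the efficacy-population share. This requires only completion of Cycle 1 plus post-cycle blood and marrow. Visit 34 is 64 − 22 = 42 days and three infusions later, so attendance could be lower. In the other direction, 7 of the 17 patients at 1.7 mg/kg had not withdrawn at the cut-off. Without that cohort the share is 17/30 = 56.7%, or about 34 of 60.
- 21.1%, the PK share after six infusions. It counts subjects in an interim analysis, not attendance at a visit.

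The second and third come from the one-shot schedule.

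**5. Precision if no patient is positive.** The exact two-sided 95% upper limit for 0 of n is 1 − 0.025^(1/n).

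| Share reaching Visit 34 | Results among 60 | No result | Upper limit for 0 positives |
|---|---|---|---|
| 70% | 60 × 0.70 = 42 | 18 | 1 − 0.025^(1/42) = 8.4% |
| 46.8% | 60 × 0.468 ≈ 28 | 32 | 1 − 0.025^(1/28) = 12.3% |
| 21.1% | 60 × 0.211 ≈ 13 | 47 | 1 − 0.025^(1/13) = 24.7% |

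These limits reflect sampling error only. They do not allow for differences between patients with and without a result.

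**The case against.** **The size of the loss is not known.** A reader might take the 85.1% early withdrawal, or the 8 of 38, to mean that only 15-21% will reach Visit 34 and that most patients will have no result. The documents do not support that. The 85.1% is undated withdrawal from the study, under versions in which patients with benefit went on to monthly infusions, so some withdrawals may fall after Day 64. Only 47 − 40 = 7 patients had not withdrawn, yet 8 had PK data after six infusions. Unless the two data cuts differ, at least one withdrawn patient had received all six. The PK count may also reflect which samples had been analysed. The ramp-up schedule was introduced to reduce early severe toxicity and may retain more patients. This part of the objection stands, and it is why a range is shown.

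**Patients who stop for infusion reactions are not shown to be the most informative.** A reader might infer that they are. Section 6.3 says the severe events arose at the first or second dose, and the experts suggested cytokine storm, monocyte-macrophage activation and target-cell lysis. Antibodies are not mentioned. Section 8.4.7 also lets some patients resume after an interruption, and they can still reach Visit 34. The inference should not be drawn.

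**Day 64 is a sensible time for the assay.** The longest mean half-life reported after repeat dosing is 146.4 h (6.2.4.3). 28 × 24 / 146.4 = 4.6 half-lives, so little drug should remain. Earlier samples may contain drug or precede antibody formation, and pooling them with Day 64 samples would blur the estimate. This argues for keeping Visit 34 and reporting other samples separately. It does not argue for leaving withdrawn patients unsampled.

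**Weight.** This is a descriptive secondary endpoint in a Phase I study, and 8.4.3.1 names safety, PK and PD data as the basis for escalation, not antibodies. That limits the priority of the point.

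**Conclusion.** The point holds as a gap in the sampling schedule. Patients who withdraw before Visit 34 have no scheduled post-baseline antibody result and fall out of a secondary endpoint. This follows from three agreeing passages and the End of Study list, and needs no assumption about rates.

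The size does need one. Between about 13 and 42 of 60 treated patients would have a result, depending on the share assumed to reach Day 64, with upper limits of 24.7% to 8.4% if none is positive. The claim that most patients will be missed is one possible outcome in that range and is not established. The selection problem remains at the favourable end, where about 18 of 60 would still lack a result.

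The change is worth making because it is cheap and the data cannot be obtained later. It does not affect the primary endpoints or dose escalation.

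**What to change.** Amend flow-chart note k, the synopsis and 8.5.1 together:

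- Keep Visit 34 as the main post-baseline time point.
- Add an immunogenicity sample at the End of Study or withdrawal visit for patients with no Visit 34 sample.
- Where such a patient is still being followed, add a sample at the existing follow-up of at least ten weeks after the last dose (8.6.6), which is less exposed to residual drug.

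In the SAP, define the denominator as treated patients with at least one post-dose sample. Show Visit 34 and early-withdrawal samples separately, by time since first and last dose. Flag samples that may contain residual drug or were taken too early for antibodies to have formed. Report the number treated who have no post-dose sample.

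The cost is one tube and one assay per added sample, and blood is already drawn at the End of Study Visit. Early negatives will be less conclusive, and patients who die or do not attend will still be missing, so coverage improves but will not be complete.
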